9.5.3.1.1 Stool grading System

Stools will be graded according to the following criteria:

Grade 1 = firm, formed

Grade 2 = soft but still formed

Grade 3 = thick liquid

Grade 4 = thin liquid

Grade 5 = clear or translucent, watery

The end of a diarrheal episode occurs when a subject does not pass any grade 3-5 stool within 24 hours.

9.5.3.1.2 Diarrhea definitions

Diarrhea will be rated according to the following criteria:

Mild	2-3 grade 3-5 stools in 24 hours and \leq 400 grams of grade 3-5 stools passed in a 24-hour period
Moderate	4-5 grade 3-5 stools in 24 hours or $>$ 400-800 grams of grade 3-5 stools passed in a 24-hour period
Severe	\geq 6 grade 3-5 stools in 24 hours or $>$ 800 grams of grade 3-5 stools passed in a 24-hour period

Up to 3 stools and/or rectal swabs each day will be cultured. Fecal cultures will be performed by the Enterics lab at JHSPH. Stools or swabs for culture will be taken to the JHSPH laboratory, where they will be inoculated directly onto MacConkey agar and onto MacConkey agar that had incorporated streptomycin selective for the inoculum strain. Up to 10 colonies will be agglutinated using specific antisera. The level of fecal shedding (cfu per gram of stool) will be assessed by quantitative stool cultures on Days 2 and 4 post-challenge.

9.5.3.1.3 ETEC Disease Severity

A three-component disease score utilizing objective signs, subjective symptoms and stool output will be analyzed for the entirety of the clinical illness (Table 7). The scoring goes from 0 (no diarrhea and no other signs or symptoms) to the maximum of 8 (severe ETEC disease) [31].

Table 7. Disease Severity Score Components

Parameter	Outcome	Score
Objective signs	>1 episode of vomiting/24 hours OR any fever	2
	1 episode of vomiting AND no fever	1
	No vomiting AND no fever	0
Subjective symptoms	Moderate-severe lightheadedness OR Severe nausea, malaise, headache or abdominal cramps	2
	Mild lightheadedness OR Mild-moderate nausea, malaise, headache or abdominal cramps	1
	No 'subjective symptoms'	0
Diarrhea score	>1000 grams of grade 3-5 stool OR >12 grade 3-5 stools in 24 hours	4
	>600 to \leq 1000 grams of grade 3-5 stool OR >7 to 12 grade 3-5 stools in 24 hours	3
	>400 to \leq 600 grams of grade 3-5 stool OR >4 to \leq 7 grade 3-5 stools in 24 hours	2
	>0 to \leq 400 grams of grade 3-5 stool OR 1 to 4 grade 3-5 stools in 24 hours	1
	No grade 3-5 stools	0

1 gram of grade 3-5 stool is considered equivalent to 1 mL of grade 3-5 stool.

9.5.3.1.4 ETEC Disease-specific solicited events

ETEC disease-specific solicited events will start being collected after challenge and will be assessed during inpatient physical examinations. Between Challenge and discharge, these pre-defined solicited events will be reported as adverse events and their relationship to the challenge strain, study procedures and/or antibiotics will be determined by the PI or designee.

ETEC Disease-specific subjective solicited events include the following symptoms:

- Malaise
- Loss of appetite
- Headache
- Chills
- Nausea
- Abdominal pain
- Abdominal cramps
- Myalgia
- Arthralgia
- Urgency of defecation
- Lightheadedness

The following solicited events will be documented via objective clinical assessments during the inpatient challenge phase:

1. Diarrhea (via stool logs)
2. Hypovolemia
3. Fever (oral temperature $\geq 100.4^{\circ}\text{ F}$)
4. Vomiting

Table 8. Severity rating of ETEC Disease-specific expected events

Event	Severity ^a	Parameter
Diarrhea, based on highest output of loose ^b stools in any 24-hour period. (A diarrhea episode ends when there is a 24-hour window with no grade 3-5 ^b stools.)	1	Mild: 2-3 loose ^b stools in 24 hours and ≤ 400 grams of loose ^b stools passed in a 24-hour period
	2	Moderate: 4 to 5 loose ^b stools in 24 hours or >400 -800 grams of loose ^b stools passed in a 24-hour period
	3	Severe: 6 or more loose ^b stools in 24 hours or >800 grams of loose ^b stools passed in a 24-hour period
	4	Potentially life-threatening
Fever ^c	1	$100.4^{\circ}\text{F}-101.1^{\circ}\text{F}$ ($38.0-38.4^{\circ}\text{C}$)
	2	$101.2^{\circ}\text{F}-102.0^{\circ}\text{F}$ ($38.5-38.9^{\circ}\text{C}$)
	3	$102.1^{\circ}\text{F}-104^{\circ}\text{F}$ ($39.0-40.0^{\circ}\text{C}$)
	4	$>104^{\circ}\text{F}$ ($>40.0^{\circ}\text{C}$)
Vomiting	1	One episode within a 24-hour period
	2	Two episodes within a 24-hour period
	3	More than two episodes within a 24-hour period
	4	Potentially life-threatening consequence of emesis

^a1=mild; 2=moderate; 3=severe 4=potentially life-threatening.

^bGrades 3-5 stools are considered loose

^cOral temperature; no recent hot or cold beverages, eating or physical activity. If temperature is $\geq 100.4^{\circ}\text{ F}$ every attempt should be made to repeat within 20 minutes. If the repeat temperature is WNL and the investigator feels the repeated temperature is a more accurate reflection of the participant's real temperature a fever will not be entered into the eCRF.

If an ETEC Disease-specific expected event changes in severity, it should be reported as a new event with the new severity but with the same event description. For definitions regarding severity rating and assessment of causal relationship see Sections 9.5.2.1.2, 9.5.2.1.3 and Table 8.

For other events including other ETEC disease-specific expected events where no pre-specified definition of severity is available, the Investigator will assess the severity of events using his/her clinical expertise and judgement based on the most appropriate description stated in Section 9.5.2.1.2.

9.5.3.1.5 Subject's assessment of impact of ETEC illness on daily activity

At Day 6 the subject will answer the following questions:

1. If traveling for vacation or business, would you have changed your itinerary?
2. Would you have stayed in bed (if so, how long)?

9.5.4 Additional assessments

9.5.4.1 Prior and concomitant medications

Medications taken by the subjects within 28 days prior to study screening until the follow-up visit (Day 29) will be documented in the subject's medical record and recorded in the eCRF. Prescription medications, over-the-counter (OTC) medications, and herbal products should be asked for.

Prior and concomitant medication will be documented at the Screening visit. Changes in prior/concomitant medication compared to Screening will be documented throughout the study. For detailed information on prohibited and concomitant medication to be administered during the study, refer to Section 9.4.8.

Medication that was stopped before baseline (Day 1) will be classified as 'prior medication'. Medications used from Day 1 will be classified as 'concomitant medication'.

9.5.5 Exploratory assessments

- Immunogenicity of the challenge with enterotoxigenic *E. coli* (ETEC) strain E24377A will be evaluated as shown below:
 - Serum IgA and IgG antibody response to LT, CS1 and CS3 will be assessed.
 - ALS IgA antibody response to LT, CS1 and CS3 will be assessed.
 - Fecal IgA antibody response to LT, CS1 and CS3 will be assessed.
IgA and IgG antibody levels will be determined by ELISA.
 - Systemic and intestinal inflammatory biomarkers will be evaluated.
- Fecal shedding (colony forming units per gram of stool) of the E24377A challenge strain will be evaluated post-challenge.

9.5.6 Schedule of Procedures

9.5.6.1 Screening

9.5.6.1.1 Screening according to general screening protocol

Subjects may be consented to a general screening protocol as per Section 9.3.3.

9.5.6.1.2 Study specific Screening (Day -60 to -2)

Healthy, potentially eligible and willing participants will be invited back to complete study specific screening.

The following assessments/procedures will be carried out:

- The participant will be provided information about the study, pass a comprehension test (see section 5.3) and provide signed informed consent before any study specific procedures are initiated
- Obtain demographic data including gender, race, height, weight, body mass index (BMI), date of birth and previous SARS-CoV-2 vaccination(s)
- Review medical history collected during CIR200 screening
- Review history of all current medications as well as those taken within the past 28 days
- Obtain responses to Functional Bowel Disorder Survey. The Functional Bowel Survey is an adaptation of Rome III guidelines utilized by the CIR to screen for gastrointestinal dysfunction per the CIR guideline.
- Obtain additional IRB-approved forms, which may include, but are not limited to the Alternate Agreement, Inpatient Unit Guidelines, Correct Hand Washing Procedure, HIPAA Medical Record Release Form, HIV Test Counseling and/or COVID Vaccination Form
- Perform complete physical examination
- Vital signs (temperature, pulse and blood pressure) will be measured
- Review inclusion/exclusion criteria to the extent possible
- Collect blood and urine samples (see Section 9.5.2.2)
- Obtain pregnancy test (serum β -HCG) from people of childbearing potential

9.5.6.2 In-patient period

9.5.6.2.1 Admission (Day -1)

- Inclusion/exclusion criteria (including test for SARS-CoV-2) will be reviewed to re-assess ongoing eligibility
- Perform a complete physical examination

- Collect blood samples if the clinical chemistry and hematology labs were not performed within the previous 7 days (see Section 9.5.2.2)
- Obtain pregnancy test (serum β -HCG) from people of childbearing potential
- Concomitant medications will be reviewed
- Vital signs (temperature, pulse and blood pressure) will be measured
- Medical history will be reviewed
- Blood and fecal samples will be collected for immunogenicity endpoints (exploratory)

9.5.6.2.2 Challenge day (Day 1)

On the day of challenge, subjects will consume a light breakfast and then initiate a 90-minute fasting period.

The following assessments/procedures will be carried out before challenge:

- Eligibility criteria will be re-confirmed
- A focused physical examination and evaluation will be performed to ensure that there are no changes from admission and no exclusionary conditions have arisen
- Urine β -HCG pregnancy test for people of childbearing potential if serum results from admission day (Day -1) are not available
- Blood and fecal samples will be collected for immunogenicity endpoints (exploratory) before challenge if not taken on Day -1.
- Concomitant medications will be reviewed
- Approximately 1 minute prior to challenge, subjects will drink 120 mL sodium bicarbonate buffer
- For the challenge, subjects will drink 30 mL of the sodium bicarbonate buffer containing approximately 4×10^9 cfu of the ETEC strain E24377A.
- Subjects will not be redosed if they have emesis after challenge, however this will be documented.
- Subjects will continue fasting for an additional 90 minutes post challenge
- Vital signs (temperature, pulse, blood pressure) be recorded 30 minutes after challenge.
- All stools will be collected for weighing and grading after challenge. Should there be grade 3-5 stools after challenge, they will be saved for culture.
- Record any AEs, AESIs and SAEs

9.5.6.2.3 Post Challenge phase (Day 2 to 8)

- Daily medical interview (including assessment of ETEC disease-specific solicited events) and focused physical examination
- Vital signs (temperature, pulse and blood pressure) will be measured at least 3 times daily

- All stools will be collected for weighing and grading. Up to 3 stool samples will be sent daily for culture. If a volunteer is unable to provide samples, they will be asked to provide a self-collected rectal swab (up to 3 per day). (If the participant does not produce a stool or enough stool on any day to obtain all samples, this will not be considered a protocol deviation.)
- Record any AEs, AESIs and SAEs
- Changes in concomitant medications will be captured
- Antibiotic treatment will be started on Day 6 (5 days after challenge) or according to criteria for early antibiotic treatment (see Section 9.4.8.2)
- Collect blood samples on Days 3, 4 and 8 for immunogenicity endpoints (exploratory)
- Collect daily fecal samples for immunogenicity endpoints (exploratory)
- Collect ETEC Impact on ADLs survey responses on Day 6

9.5.6.3 Discharge (Day 9)

Routine discharge is planned for study day 9. Procedures that must be completed prior to discharge include:

- Vital signs (temperature, pulse and blood pressure) will be measured (at least 1 set)
- Medical interview (including assessment of ETEC disease-specific solicited events) and focused physical examination
- Record any AE, AESIs and SAEs
- Changes in concomitant medications will be captured
- All stools will be collected for weighing and grading until participant is eligible for discharge. Collections will end once discharge criteria is met.

Some participants may be discharged prior to Day 9. Their discharge will also follow these procedures, with the addition of being dispensed any remaining doses of antibiotics and directions for their use. Early discharge participants will also be given directions for outpatient follow-up visits on Days 7 and 8 if applicable, see section 9.5.6.7.

Volunteers who do not meet discharge criteria by day 9 will remain on the unit and will continue to undergo the procedures listed in section 9.5.6.3.

9.5.6.4 Out-patient follow-up Visit (Day 29 ± 4 days)

Procedures this day will include:

- Vital signs (temperature, pulse and blood pressure) will be measured
- Urine β-HCG pregnancy test for people of childbearing potential
- Medical interview and review of concomitant medications and AEs/AESIs/SAEs
- Focused Physical exam if participants have complaints/AEs or symptoms

- Collect blood and fecal samples for immunogenicity endpoints (exploratory)

9.5.6.5 Follow-up contact (Day 180 ± 14 days)

This medical interview/contact will occur by phone and will include:

- Obtain responses to the Functional bowel disorder survey
- Participants will be questioned about their health status, including any new chronic illnesses, AESIs or SAEs

9.5.6.6 Unscheduled Visit

If an unscheduled visit occurs, a member of the clinical study team will interview and evaluate the subject to determine the cause of the visit and provide care as needed and information documented in the source data. Adverse events and concomitant medications will be reviewed. Clinical laboratory tests and physical examination may be done as indicated.

9.5.6.7 Early Discharge Outpatient Visits (Day 7 & 8)

If the participant meets the discharge criteria early and are determined to be eligible by an investigator, they will be considered discharged. Participants will be offered the options of remaining on the unit as a boarder or leaving the unit and returning on Day 7 and 8 (as applicable) to complete the outpatient procedures per the Schedule of Events (Table 1). Boarders who remain on the unit will undergo the procedures required for outpatient visits. Boarders will continue to have their concomitant medications and antibiotics administered by staff and recorded on the CRF. Early discharged participants will be given stool collections kits so that they may bring fecal samples to outpatient visits. Fecal samples will be collected, processed and sent per Table 1. Stool cultures will not be sent.

If the participant does not meet the discharge criteria but elects to withdraw early from the inpatient period and is amendable to returning for any or all future study visits, they will be considered “off treatment” but not terminated from study

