After discharge from the in-patient unit, all subjects will attend the scheduled follow-up visit/contact on an out-patient basis on Day 29 (physical visit) and Day 180 (phone).

Test Product, dosage and mode of administration

Each subject will drink 120 mL of sodium bicarbonate buffer (in order to neutralize gastric acidity) followed one to two minutes later with 30 mL of sodium bicarbonate buffer containing approximately 4×10^9 cfu of the challenge strain E24377A. All subjects will have fasted for approximately 90 minutes before challenge and for approximately 90 minutes after challenge.

Reference Therapy, dosage and mode of administration (if applicable)

Not applicable in this study.

Duration of treatment

All subjects will receive a single administration of E24377 at baseline (Day 1). The study period includes a 5-10 day in-patient period that will be followed by a 3-week outpatient follow-up period and there will be a final contact (phone call) approximately 6 months after challenge.

Duration of subjects' involvement in the study

The total duration of any subject's participation in the study will be up to around 35 weeks including a screening period of up to 60 days, a 5-10 day in-patient period and 26 weeks (approximately 6 months) follow-up after challenge.

Efficacy assessments

Clinical indicators will include the incidence, severity, and time to onset of diarrhea, the incidence and duration of positive stool cultures, the incidence of moderate and severe ETEC illness, evaluation of the number and weight of grade 3-5 stools, and the incidence of malaise, loss of appetite, headache, chills, fever, nausea, abdominal pain, abdominal cramps, myalgia, arthralgia, urgency of defecation, vomiting and lightheadedness.

Stool grading criteria: grade 1 = firm, formed; grade 2 = soft but still formed; grade 3 = thick liquid; grade 4 = thin liquid; grade 5 = clear or translucent, watery.

Safety assessments

Safety evaluations will include documentation of adverse events and key vital sign measurements.

Statistical methods

No formal statistical testing is planned for this study.

The proportion of subjects with moderate and severe diarrhea will be presented with 95% confidence intervals.

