8.2.1 Secondary Clinical endpoints

- Severe diarrhea defined as ≥ 6 grade 3-5 stools or > 800 g of grade 3-5 stools passed within a rolling 24-hour period.
- ETEC disease severity: 3-component disease score (total score) utilizing objective signs, subjective symptoms and stool output [31].
- Incidence of diarrhea (≥ 2 grade 3-5 stools in a 24-hour period) of any severity.
- Total weight of grade 3-5 stools passed per subject over the 120-hour observation period.
- Number of grade 3-5 stools per subject over the 120-hour observation period.
- Occurrence of other ETEC Disease-specific events (malaise, loss of appetite, headache, chills, fever, nausea, abdominal pain, abdominal cramps, myalgia, arthralgia, urgency of defecation, vomiting and lightheadedness).
- Self-assessment of ETEC illness impact on daily activity at Day 6.

- Time (relative to challenge) to the first grade 3-5 stool of the first diarrhea episode.
- Time (relative to challenge) to meeting the primary endpoint (time of the stool that meets the criteria for at least moderate diarrhea).
- Requirement of early (prior to Day 6) antibiotic treatment.
- Requirement of IV fluids.
- Maximum 24-hour grade 3-5 stool output (weight).
- Maximum number (24-hour) of grade 3-5 stools.

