### 2.6.3. ETEC Impact on Activities of Daily Living (ADLs)

On Day 6, subjects will answer the following two questions:

1. If traveling for vacation or business, would you have changed your itinerary?
  - Subjects will report "Yes" or "No".
2. Would you have stayed in bed (if so, how long)?
  - Subjects will report "Yes" or "No". If a subject reports "Yes", they will also report the amount of time they would have stayed in bed in hours and minutes.

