#### 5.4. ETEC Disease Severity Score

Summary statistics (mean, standard deviation, median, minimum, and maximum) of ETEC disease severity score will be presented by component sub-score and total score in Table 16. Individual data contributing to ETEC disease severity score will be listed in Listing 7.

#### 5.5. Self-Assessment of ETEC Illness Impact on Daily Activity at Day 7

Number and percentage of subject responses on ADLs are presented in Table 17.

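### The Day 6 daily-activity survey has no collection route for subjects discharged before Day 6, so this secondary endpoint can be missing selectively in early-treated subjects

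*Protocol*

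**What the plan says.** The survey is a secondary clinical endpoint with one time point. Protocol 8.2.1 lists "Self-assessment of ETEC illness impact on daily activity at Day 6", and 9.5.3.1.5 repeats it: "At Day 6 the subject will answer the following questions". The only collection instruction is in the in-patient list of Protocol 9.5.6.2.3: "Collect ETEC Impact on ADLs survey responses on Day 6". SAP 2.6.3 agrees: "On Day 6, subjects will answer the following two questions". The heading of SAP 5.5 does not: "Self-Assessment of ETEC Illness Impact on Daily Activity at Day 7".

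Discharge is tied to conditions, not to a day. Protocol 9.4.8.2 asks for two stools negative for the challenge organism, two antibiotic doses, and absent or improved symptoms. Protocol 7.3.2 allows both cultures to come from one day. The synopsis foresees short stays: "The study period includes a 5-10 day in-patient period".

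For those who go early, Protocol 9.5.6.3 states: "Early discharge participants will also be given directions for outpatient follow-up visits on Days 7 and 8 if applicable". Protocol 9.5.6.7 offers a choice between boarding on the unit and leaving, then "returning on Day 7 and 8 (as applicable". Boarders are to have the procedures of the outpatient visits. The survey is not named in 9.5.6.3 or 9.5.6.7, nor in the Day 29 and Day 180 lists (9.5.6.4, 9.5.6.5).

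SAP 3.5 plans no imputation because little missing data is expected. SAP 3.1.1 bases percentages on non-missing responses.

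**The concern.** A subject who is treated early, recovers and is discharged before Day 6 has no instruction anywhere to answer the survey. This can happen only to early-treated subjects (withdrawals aside). Everyone else starts antibiotics on the morning of Day 6 and needs two doses before discharge, so they are still on the unit that day.

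The loss would therefore not be random. Early treatment is triggered by more than 800 g of loose stool in 24 hours, 48 hours of moderate output, diarrhea with at least two listed symptoms, high fever, or a clinician's judgement. Such subjects are plausibly the most likely to say that they would have changed an itinerary or stayed in bed. With 25 to 30 subjects, one answer is worth 3.3 to 4 points (1/30 to 1/25), and an answer not taken at the time cannot be recovered as defined.

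**Working it through.** The plan gives no figure of its own for this endpoint, so there is nothing to reproduce. The check has three parts.

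**1. Can discharge precede Day 6?**
- Length of stay: there is no Day 0. Days -1 and 1 to 9 make 10 days, which matches routine discharge on Day 9. On the same count a 5-day stay covers Days -1, 1, 2, 3 and 4 and ends on Day 4. Counted from challenge, it ends on Day 5. Both precede the survey.
- Clinical timing: mean time to illness was 26 to 47 h (Protocol Table 3), and Protocol 7.3.2 says illness generally improves within 24 h of antibiotics. That gives 26 + 24 = 50 h to 47 + 24 = 71 h, against about 120 h from challenge to Day 6. If treatment starts only after 48 h of moderate output, it gives 98 to 119 h, with little margin. The time from onset to meeting the other criteria, and culture turnaround, are not in the documents.

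So discharge before Day 6 is permitted and feasible. How often it would occur cannot be derived.

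**2. How many surveys could be lost?**
- N = 25 to 30 (Protocol 9).
- e, the early-treated share, from Protocol Table 3: 8/16 = 50% in one study. The other reports 12/15 = 80%, but it challenged 20 subjects. On that base the share is 12/20 = 60%, if no one outside the 15 was treated.
- f, the share of early-treated subjects who leave before Day 6 unsurveyed: assumed 10%, 25% or 50%.

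Expected number missing m = N × e × f; lowest from 25 × 0.5, highest from 30 × 0.6. Best-case to worst-case width for the Yes percentage = m/N = e × f.

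| f | m, lowest | m, highest | width (points) |
|---|---|---|---|
| 10% | 12.5 × 0.10 = 1.25 | 18 × 0.10 = 1.8 | 5 to 6 |
| 25% | 12.5 × 0.25 = 3.1 | 18 × 0.25 = 4.5 | 12.5 to 15 |
| 50% | 12.5 × 0.50 = 6.25 | 18 × 0.50 = 9 | 25 to 30 |

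**3. What would that do to the estimate?**
Assume Yes in a = 80% of early-treated and b = 30% of other subjects, with leavers like other early-treated subjects.
- Full = e·a + (1 − e)·b
- Observed = [e(1 − f)·a + (1 − e)·b] / (1 − e·f)

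| e | f | Full | Observed | Difference (points) |
|---|---|---|---|---|
| 0.5 | 0.10 | 0.550 | 0.510/0.950 = 0.537 | −1.3 |
| 0.5 | 0.25 | 0.550 | 0.450/0.875 = 0.514 | −3.6 |
| 0.5 | 0.50 | 0.550 | 0.350/0.750 = 0.467 | −8.3 |
| 0.6 | 0.10 | 0.600 | 0.552/0.940 = 0.587 | −1.3 |
| 0.6 | 0.25 | 0.600 | 0.480/0.850 = 0.565 | −3.5 |
| 0.6 | 0.50 | 0.600 | 0.360/0.700 = 0.514 | −8.6 |

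The sign depends on the leavers: observed − full = (m/N) × (Yes rate in responders − Yes rate in leavers). For e = 0.5 and f = 0.25 this is 0.125 × (0.514 − 0.80) = −0.036, as in the table. If the leavers answered Yes at only 30%, it would be 0.125 × (0.514 − 0.30) = +0.027, an overestimate of 2.7 points.

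**The case against.** **Boarders.** A reader might infer that no early-discharged subject has any contact on Day 6. The documents do not support that: Protocol 9.5.6.7 offers boarding, and staff administer boarders' medication, so they could be asked. What remains is that boarders are assigned only outpatient-visit procedures, and no text tells staff to survey them. Subjects discharged on Days 6 to 8 are unaffected.

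**Day 7.** If the SAP 5.5 heading governed, the survey would coincide with a return visit and most of the gap would close. But Protocol 8.2.1, 9.5.3.1.5 and 9.5.6.2.3 and SAP 2.2.2 and 2.6.3 all say Day 6, and 9.5.6.7 names no survey on Day 7. The heading is an inconsistency to settle, not a remedy.

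**Direction.** It is tempting to call the result biased downward. The documents do not establish that. Leaving early requires improvement and two negative cultures, which selects quicker recoverers; slower early-treated subjects stay and answer. Early treatment can also rest on clinician judgement alone, and no survey data by treatment status are given.

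**Consequence.** This is one of 13 secondary clinical endpoints in a single-arm descriptive study without formal testing. Sampling error is larger than the shift: 12 Yes among 20 responders has an exact 95% interval of 36% to 81%. The SAP Table 17 mock-up also prints N and the Yes and No counts, so the number missing can be worked out by subtraction. All of this stands, and it keeps the point small. It does not supply the missing collection instruction.

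**Conclusion.** The gap is real and minor. Followed as written, the plan can lose the Day 6 survey in early-treated subjects discharged before that day: those who leave have no contact on Day 6, and those who board have no stated survey.

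The size rests on an early-treated share of 50–60% and an assumed 10%, 25% or 50% of those leaving unsurveyed: an expected 1–2, 3–4.5 or 6–9 surveys lost. With assumed Yes rates of 80% and 30%, the reported percentage would be about 1, 4 or 8–9 points too low. An underestimate is the likelier direction but not a certain one.

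A reader might also take from Protocol Table 3 that up to 80% of challenged subjects were treated early. That figure is 12 of 15 in a study of 20 and should not be applied to everyone challenged.

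The primary endpoint is not affected. This is a cheap improvement.

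**What to change.** - For any subject discharged before Day 6, boarders included, collect the two questions at discharge, or on Day 6 by phone or in person. State this in Protocol 9.5.3.1.5, 9.5.6.3 and 9.5.6.7 and in SAP 2.6.3.
- Reconcile the Day 7 heading of SAP 5.5 with Day 6, and confirm that the survey mark in both schedules of events sits under the intended day.
- Add a missing row to SAP Table 17, as the Table 24 mock-up already does with its not-reported category. State the denominator: Table 17 defines N as the Full Analysis Set, while SAP 3.1.1 uses non-missing responses. Showing the number missing by early-treatment status would let readers judge the selection.

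The cost is a two-question form or a short call for a few subjects. If the questions are asked at discharge, those subjects answer on a slightly different recall day, which a table footnote can record. No treatment or discharge rule changes.
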